2.4.6 Analyses of pharmacokinetic and pharmacodynamic variables

The baseline value of PK and PD variables is the original baseline from the parent study.

2.4.6.1 Pharmacokinetic analysis

The PK analyses will be performed for each analysis set ([Section 2](#)) of PK population ([Section 2.3.3](#)).

For the full analysis set, PK analysis will be presented in the PK population by visit according to the dose regimen (100 mg q2w or 200 mg q2w or 300 mg q4w) to which the PK sampling is exposed. That is if a patient is switched from 100 mg q2w to 200 mg q2w, the results from PK sampling before or on date of the switch will be summarized in 100 mg q2w group and results from PK sampling after the switch will be summarized in 200 mg q2w group. Similarly, if a patient is switched from 100 mg q2w to 300 mg q4w, the results from PK sampling before or on date of the switch will be summarized in 100 mg q2w group and results from PK sampling after the switch will be summarized in 300 mg q4w group.

Similarly for modified analysis set, PK analysis will be presented in PK population by visit according to the dose regimen (100 mg q2w, 200 mg q2w) to which the PK sampling is exposed at each visit.

Serum concentrations of dupilumab will be summarized using arithmetic and geometric means, SD, standard error of the mean (SEM), coefficient of variation (CV), minimum, median and

maximum by visit. If date and/or time of the drug intake and/or sampling are missing, then the concentration will not be taken into account. For the patients from the Dupilumab arm of parent study, one-half of LLOQ will be used if the pre-dose concentration values at Week 0 of LTS14424 are below the lower limit of quantitation (LLOQ = 78 ng/ml); For the patients from the Placebo arms of parent study, the pre-dose concentration value at Week 0 of LTS14424 should use 0 if the pre-dose concentration values at Week 0 of LTS14424 are below the lower limit of quantitation. Values will be expressed in the tables with no more than three significant figures.

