11.4 STATISTICAL METHODS

For each analysis population defined in [Section 11.3](#), the planned analyses will be conducted in the following two analysis sets, respectively.

The full analysis set for each analysis population will include all data observed in the study.

The modified analysis set for each analysis population will censor the data observed on or after the first dose of 300 mg q4w for the patients in this analysis population who were exposed to the 300 mg q4w regimen. Particularly, the patients who will initiate the treatment on 300 mg q4w regimen since Week 0 of LTS14424 study will be excluded from the modified analysis set.

For each analysis set, the planned analyses will be presented by the group of patients according to their actual treatment groups in the parent study EFC14153, specifically, 'Placebo-Dupilumab', 'Dupilumab-Dupilumab', and 'All'.

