11.4.4.1 Pharmacokinetic analysis

The PK analyses will be performed in the two analysis sets for PK population as defined in [Section 11.4](#) by the dose regimen. The baseline value of each applicable PK variable is the original baseline from the parent study. Serum concentrations of functional dupilumab will be summarized using arithmetic and geometric means, SD, standard error of the mean (SEM), coefficient of variation, minimum, maximum, and median.

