2.4 STATISTICAL METHODS

Generalities

For each analysis set defined in [Section 2](#), the planned analyses will be presented by below treatment categories according to the actual treatment groups in the parent study EFC14153:

- Placebo-Dupilumab, defined as the patients who have been in the actual placebo arm of the parent study and exposed to dupilumab in LTS14424.
- Dupilumab-Dupilumab, defined as the patients who have been in the actual dupilumab arm of the parent study and exposed to dupilumab in LTS14424.
- All, defined as all patients from Placebo-Dupilumab and Dupilumab-Dupilumab categories.

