2.4.6.2 Pharmacodynamics

For all biomarkers noted in the [Section 2.1.7](#), the biomarker will be analyzed for each analysis set ([Section 22](#)) of the safety population by the treatment category.

For eosinophil count and serum total IgE, descriptive statistics (including number, mean, median, standard deviation, Q1, Q3, minimum and maximum), change from baseline and percentage change from baseline over visits will be presented. In addition, the mean, mean change from baseline, mean percentage change from baseline with corresponding standard error will be plotted across visits. For biomarkers showing substantial skewness, the geometric means will also be presented.

For antigen-specific IgEs with a positive (≥ 0.35 IU/mL) incidence of greater than 25% at baseline, values at each visit, absolute change from baseline and percent changes from baseline will be summarized in descriptive statistics. Values reported as below the LLOQ will be imputed as a value one half of the LLOQ.

Number and percentage of patients with no positive (≥ 0.35 IU/mL) antigen-specific IgE result, with positive (≥ 0.35 IU/mL) result for only one antigen, and with positive (≥ 0.35 IU/mL) results for at least two antigens will be summarized by treatment group and time point. Same analysis will also be performed using LLOQ as the threshold.

For eosinophil count, with subgrouping the patients into original baseline EOS ≤ 0.5 Giga/L and > 0.5 Giga/L, the mean change from baseline will be plotted over visits for each of the two subgroups and overall. And table showing number (%) of patients who have peak post-baseline EOS count ≥ 1 Giga/L, ≥ 3 Giga/L and ≥ 5 Giga/L will be presented for each of the two subgroups and overall.

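### The Week 0 PK summary plans a geometric mean on data that include imputed zeros, and its grouping does not separate ex-placebo from ex-dupilumab children

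*SAP*

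**What the plan says.** **General grouping rule.** SAP 2.4 states that "the planned analyses will be presented by below treatment categories according to the actual treatment groups in the parent study EFC14153". The categories are Placebo-Dupilumab, Dupilumab-Dupilumab and All. Protocol 11.4 has the same rule: "the planned analyses will be presented by the group of patients according to their actual treatment groups in the parent study EFC14153".

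**PK grouping.** SAP 2.4.6.1 says that "PK analysis will be presented in the PK population by visit according to the dose regimen" to which the sample was exposed. Protocol 11.4.4.1 likewise plans PK "by the dose regimen. The baseline value of each applicable PK variable is the original baseline from the parent study". Neither section mentions the parent category. The sections beside it do: SAP 2.4.6.2 analyses biomarkers in each analysis set "of the safety population by the treatment category", and SAP 2.4.7 does the same for ADA.

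**Values below the LLOQ (78 ng/mL) at Week 0.** For ex-dupilumab children, "one-half of LLOQ will be used if the pre-dose concentration values at Week 0 of LTS14424 are below the lower limit of quantitation". For ex-placebo children, under the same condition, "the pre-dose concentration value at Week 0 of LTS14424 should use 0".

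**Statistics.** "Serum concentrations of dupilumab will be summarized using arithmetic and geometric means", together with SD, SEM, CV, minimum, median and maximum, by visit. No exception is made for Week 0 or for zeros.

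**Who is in the table.** A pre-dose Week 0 sample is scheduled (SAP 2.1.5). The PK population requires an evaluable sample after the first LTS14424 dose and has no restriction by parent arm (SAP 2.3.3).

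**The concern.** Two instructions in one paragraph do not work together: zeros are imputed, and a geometric mean is requested for the same visit. Separately, the two parent arms are in quite different states at Week 0. One has not yet received dupilumab, while most of the other has just finished a year of it. The SAP recognises this by giving the arms different LLOQ rules, but the PK section names no display that keeps them apart.

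Systemic exposure is a stated secondary objective. If the section is programmed literally, the Week 0 row will hold a geometric mean that is missing or 0, or one from which zeros were dropped without notice, beside an arithmetic mean that describes neither arm. A programmer would also have to choose between the general rule and the PK section without guidance.

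**Working it through.** The plan gives no figure to reproduce on this point. The check is direct arithmetic on the stated rules.

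**Inputs from the documents**
- LLOQ 78 ng/mL = 0.078 mg/L; half of it is 0.039 mg/L (SAP 2.4.6.1).
- Mean steady-state troughs of 28.3 and 58.5 mg/L for 200 mg and 300 mg q2w in adults (protocol 4.2). No pediatric trough is given, so these serve only as illustration.

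**Assumptions**
- Share p of ex-placebo children in a regimen group: not in the documents; range 1% to 50%.
- All ex-placebo Week 0 values are below LLOQ.
- Ex-dupilumab values are log-normal with a CV of 50%.

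**Step 1: geometric mean.** GM = exp(mean of ln x). With one zero, ln(0) is minus infinity, so the GM is undefined on the log scale, or 0 as a limit, for any p above 0. This needs no assumption about p or trough level. For a trough mean of 28.3 mg/L the ex-dupilumab GM is 28.3/√(1 + 0.5²) = 25.3 mg/L. Software that silently drops zeros would print 25.3 for the whole group.

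**Step 2: arithmetic mean.** Pooled mean = (1 − p) × ex-dupilumab mean. Pooled CV = √[(1 + 0.5²)/(1 − p) − 1].

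| p | Pooled mean, trough 28.3 | Pooled mean, trough 58.5 | Pooled CV |
|---|---|---|---|
| 1% | 28.02 | 57.92 | 0.51 |
| 25% | 21.23 | 43.88 | 0.82 |
| 1/3 | 18.87 | 39.00 | 0.94 |
| 50% | 14.15 | 29.25 | 1.22 |

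The mean can be computed, but it moves with the mix of arms rather than with exposure in either.

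**Step 3: would half of LLOQ for everyone solve it?** Pooled GM = 25.3^(1 − p) × 0.039^p, which gives 5.0, 2.9 and 1.0 mg/L at p = 25%, 1/3 and 50%. It is now defined, but it is driven by the imputed constant and the arm mix.

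**Step 4: which regimen group?** SAP 2.4.6.1 assigns a sample to the regimen it was exposed to, and a sample taken on the day of a switch to the regimen before the switch. An ex-placebo child's pre-dose Week 0 sample has been exposed to no dupilumab regimen, so its group is not defined.

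**Step 5: does the general rule rescue the row?** If Placebo-Dupilumab, Dupilumab-Dupilumab and All are applied on top of regimen, the Dupilumab-Dupilumab column is sound (mean 28.3, GM 25.3 mg/L in the illustration). The Placebo-Dupilumab GM is still undefined, and All still mixes the arms and contains zeros. Splitting alone is therefore not enough; the zeros also need a rule.

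**The case against.** The best defence is that SAP 2.4 heads the whole of 2.4.x and that protocol 11.4 agrees with it. Nothing in the PK section says regimen replaces the parent category, and it can be read as a further split. The arm-specific LLOQ rule suggests the authors had the arms in view, and SAP 2.4.7.5 allows optional concentration summaries by treatment category. A reader might infer that the plan definitely presents PK by regimen alone. The documents do not support that: the PK section omits the category and leaves its relation to the general rule open.

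Other stronger readings also fail:
- **Week 0 as the reference for exposure.** SAP 2.1.5, SAP 2.4.6 and protocol 11.4.4.1 take the parent-study baseline.
- **Week 0 as the sole view of trough.** Pre-dose samples are also scheduled at Weeks 12 and 24, with a sample at Week 52, and protocol 10.1.1 lets same-day parent EOT or EOS data stand in at Week 0.
- **Every ex-placebo child at 0 and every ex-dupilumab child at trough.** Zero applies only below LLOQ. Late COVID-19 enrollees may start up to 12 weeks after parent EOS, and the Brazilian children who stopped for vaccination may also enroll.
- **A meaningless arithmetic mean.** It is computable, as are the median and range.

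What survives is the geometric mean, which fails under either reading of the grouping, and the unresolved grouping itself.

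**Conclusion.** This is a minor point, but the text is wrong as written and not merely short of detail. Followed literally, the Week 0 geometric mean is undefined in any group with an ex-placebo child below LLOQ, whatever the allocation. An arithmetic mean pooled over the parent arms is low by exactly the ex-placebo share, if all those values are zero. A reader might be tempted to quote a 25% to 50% shortfall as a result. That is only the assumed share restated, since the documents give neither the parent allocation nor a pediatric trough.

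The reach is one visit of a descriptive secondary summary with no hypothesis test. The zero rule does not extend to later visits, and the primary TEAE endpoint does not depend on it.

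**What to change.** In SAP 2.4.6.1, add a Week 0 rule:
- Present Week 0 concentrations by parent treatment category, and within regimen for Dupilumab-Dupilumab.
- Report the geometric mean for Dupilumab-Dupilumab only.
- For Placebo-Dupilumab, report the number (%) below LLOQ in its place. Shown as one category, this also removes the need to assign these samples to a regimen.
- Give no pooled 'All' mean at Week 0.

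One further sentence should say whether the treatment categories of SAP 2.4 apply to PK at the other visits. The cost is one extra split in one table; no new data, sampling or analysis is needed.

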2.4.6.2 Pharmacodynamics

For all biomarkers noted in the [Section 2.1.7](#), the biomarker will be analyzed for each analysis set ([Section 22](#)) of the safety population by the treatment category.

For eosinophil count and serum total IgE, descriptive statistics (including number, mean, median, standard deviation, Q1, Q3, minimum and maximum), change from baseline and percentage change from baseline over visits will be presented. In addition, the mean, mean change from baseline, mean percentage change from baseline with corresponding standard error will be plotted across visits. For biomarkers showing substantial skewness, the geometric means will also be presented.

For antigen-specific IgEs with a positive (≥ 0.35 IU/mL) incidence of greater than 25% at baseline, values at each visit, absolute change from baseline and percent changes from baseline will be summarized in descriptive statistics. Values reported as below the LLOQ will be imputed as a value one half of the LLOQ.

Number and percentage of patients with no positive (≥ 0.35 IU/mL) antigen-specific IgE result, with positive (≥ 0.35 IU/mL) result for only one antigen, and with positive (≥ 0.35 IU/mL) results for at least two antigens will be summarized by treatment group and time point. Same analysis will also be performed using LLOQ as the threshold.

For eosinophil count, with subgrouping the patients into original baseline EOS ≤ 0.5 Giga/L and > 0.5 Giga/L, the mean change from baseline will be plotted over visits for each of the two subgroups and overall. And table showing number (%) of patients who have peak post-baseline EOS count ≥ 1 Giga/L, ≥ 3 Giga/L and ≥ 5 Giga/L will be presented for each of the two subgroups and overall.

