11.4.4.3 Pharmacodynamics

The biomarker analyses will be applied in the two analysis sets for safety population. The baseline value for the applicable pharmacodynamics (PD) variables is the original baseline from the parent study. For all PD parameters, the descriptive statistics (number, mean, median, SD, Q1, Q3, minimum and maximum) will be summarized over time for the raw measurements, the change from baseline, and percentage change from baseline. Summary plots (mean \pm SEM) over time on the raw measurements, change from baseline, and percentage change from the baseline will be presented for the PD parameters.

All parameters will be summarized in descriptive statistics.

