1 OVERVIEW AND INVESTIGATIONAL PLAN

1.1 STUDY DESIGN AND RANDOMIZATION

LTS14424 is a multinational, multicenter, open-label, single arm, 1-year treatment study evaluating dupilumab given subcutaneously (SC) for a period of 52 weeks. The study is designed to evaluate the long-term safety and tolerability of dupilumab in pediatric patients with asthma who participated in a previous dupilumab asthma study (EFC14153). In addition, this study was designed to collect PK, safety, and clinical response information on patients with asthma who weigh ≤ 30 kg and who are treated with dupilumab 300 mg q4w.

Patients receive their first dose of dupilumab in the LTS14424 study at Visit 1 which is Week 0 that corresponds to EOT visit (Week 52) of the parent EFC14153 study. For patients who are not able to perform the EFC14153 EOT visit onsite due to the COVID-19 pandemic, LTS14424 Visit 1 (Week 0) can occur at the EFC14153 EOS visit or for up to 12 weeks after the EFC14153 EOS visit. The initial planned treatment regimen is based on the patients' weight at enrollment in LTS14424: 200mg q2w for children > 30 kg, and 100mg q2w for children ≤ 30 kg. Protocol amendment 3 updated the dose for children ≤ 30 kg to 300 mg q4w, and all children in this weight category with at least 8 weeks remaining before the planned end of treatment period were to be switched to this dose at the time of amendment approval. All newly enrolled children with body weight ≤ 30 kg will take 300 mg q4w. At subsequent visits, for all patients whose body weight increases from ≤ 30 kg to > 30 kg, their dupilumab dose will be increased to 200 mg SC q2w and then maintained during the remaining treatment period.

Approximately 354 patients from parent study (EFC14153) will be enrolled into LTS14424 study.

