2.1 ANALYSIS ENDPOINTS

The baseline values of endpoints in LTS14424 are defined as the original baseline of the parent study, unless otherwise specified. In addition to the baseline, the pre-dose measurements at Week 0 of LTS14424 are defined as the last available measurements prior to the first IMP dose in LTS14424 study.

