3.6.1.3 Biomarker analyses

Biomarkers will be analyzed on the safety population.

For blood eosinophil count, FeNO, and serum total IgE, descriptive statistics (including number, mean, median, standard deviation, Q1, Q3, minimum and maximum), change from baseline and percentage change from baseline over visits will be presented. In addition, the mean, mean change from baseline, median percentage change from baseline will be plotted across visits.

For antigen-specific IgEs with a positive (≥ 0.35 IU/mL) incidence of greater than 25% at baseline, values at each visit, absolute change from baseline and percent changes from baseline will be summarized in descriptive statistics. Values reported as below the LLOQ (lower limit of quantitation) will be imputed as a value one half of the LLOQ.

Number and percentage of participants with no positive (≥ 0.35 IU/mL) antigen-specific IgE result, with positive (≥ 0.35 IU/mL) result for only one antigen, and with positive (≥ 0.35 IU/mL) results for at least two antigens will be summarized by time point. Same analysis will also be performed using LLOQ as the threshold.

For blood eosinophil count, with subgrouping the participants into baseline EOS ≤ 0.5 Giga/L and >0.5 Giga/L, the mean change from baseline will be plotted over visits for each of the two subgroups and overall. And table showing number (%) of participants who have peak post-baseline EOS count ≥ 1 Giga/L, ≥ 3 Giga/L and ≥ 5 Giga/L will be presented for each of the two subgroups and overall.

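### The eosinophil subgroup figure groups children by the parent-baseline count and plots change from that same count, which adds a regression-to-the-mean shift to both curves

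*SAP*

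**What the plan says.** Main SAP 2.4.6.2 (Pharmacodynamics) says of the eosinophil count: "with subgrouping the patients into original baseline EOS ≤ 0.5 Giga/L and > 0.5 Giga/L, the mean change from baseline will be plotted". An overall curve is drawn as well. The next sentence plans, for the same subgroups and overall, a table of children whose peak post-baseline count reaches 1, 3 or 5 Giga/L.

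Three places define the baseline, and they agree:

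- Main SAP 2.1: "The baseline values of endpoints in LTS14424 are defined as the original baseline of the parent study, unless otherwise specified".
- Main SAP 2.4.6: "The baseline value of PK and PD variables is the original baseline from the parent study".
- Protocol 11.4.4.3: "The baseline value for the applicable pharmacodynamics (PD) variables is the original baseline from the parent study".

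SAP 2.4.6.2 specifies nothing different, so one parent-study measurement both assigns the subgroup and is subtracted from every later count.

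Other relevant provisions:

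- **Design.** SAP 1.1 describes a "multinational, multicenter, open-label, single arm, 1-year treatment study".
- **Display.** Biomarkers are analyzed for each analysis set "of the safety population by the treatment category", that is, Placebo-Dupilumab, Dupilumab-Dupilumab and All (SAP 2.4).
- **A second pre-dose value.** SAP 2.1 adds that "the pre-dose measurements at Week 0 of LTS14424 are defined as the last available measurements prior to the first IMP dose in LTS14424 study". SAP 2.4.5 and 2.4.5.3 present this value in laboratory summaries and plots.
- **Method.** SAP 2.5.2 limits the analysis to descriptive summaries of observed data, so no model adjusts for baseline.

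Japan SAP 3.6.1.3 uses the same split at 0.5 Giga/L and the same display: "the mean change from baseline will be plotted over visits for each of the two subgroups and overall". Its baseline is the last value before the first dose (Japan SAP 3.1).

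**The concern.** A single eosinophil count mixes a child's usual level with short-term variation. Children classed above 0.5 Giga/L include some whose count was high by chance that day, and their later counts tend to be lower. The reverse holds below 0.5. When the classifying count is also the one subtracted, this drift enters the plotted change directly. No untreated arm runs alongside LTS14424 to show how much of the movement it explains, and the SAP gives no caveat.

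Eosinophilia is a selected AE grouping (SAP Table 4), and on-treatment counts above 3000 cells/µL are reported as AEs (Protocol 10.4.6). A reader may therefore use this figure to ask whether counts move differently by starting level. Part of any convergence of the two curves would be artifact. Measured against the zero line, a rise in the >0.5 group would be understated and a rise in the ≤0.5 group overstated.

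**Working it through.** The plan states no figure for this display, so there is nothing to reproduce.

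**Direction.** Let X1 be the baseline count, X2 a later count and c = 0.5. Assume no drug or time effect and an exchangeable pair. Then

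E[(X2 − X1)·1{X1 ≤ c}] = E[X2·1{X1 ≤ c < X2}] − E[X2·1{X2 ≤ c < X1}].

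The two events have equal probability. X2 exceeds c in the first and does not in the second, so the difference is positive whenever some children cross c. The group above c has the opposite sign, and the two cancel overall. No particular distribution is needed.

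**Size.** The documents give no eosinophil distribution or repeatability, so every input here is assumed: log-normal counts with equal margins, geometric mean 0.3 or 0.4 Giga/L, log-SD s of 0.7 or 0.9, and correlation r of log counts of 0.5, 0.65 or 0.8.

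With M = GM·exp(s²/2) and a = ln(0.5/GM)/s:

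- low group: baseline mean M·Φ(a − s)/Φ(a); later mean M·Φ(a − rs)/Φ(a)
- high group: M·[1 − Φ(a − s)]/[1 − Φ(a)] and M·[1 − Φ(a − rs)]/[1 − Φ(a)]

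Example with GM 0.4, s 0.7, r 0.65: M = 0.51105, a = 0.319, Φ(a) = 0.62505, Φ(a − s) = 0.35152, Φ(a − rs) = 0.44582.

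- Low: 0.51105 × 0.35152/0.62505 = 0.287; later 0.51105 × 0.44582/0.62505 = 0.365. Change +0.077 (+27%).
- High: 0.51105 × 0.64848/0.37495 = 0.884; later 0.51105 × 0.55418/0.37495 = 0.755. Change −0.129 (−15%).
- Overall: 0.625 × 0.077 − 0.375 × 0.129 = 0, to rounding.

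Over the 12 combinations:

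| Group | Smallest shift | Largest shift |
|---|---|---|
| ≤0.5 Giga/L | +0.028 (GM 0.3, s 0.7, r 0.8) | +0.163 (GM 0.4, s 0.9, r 0.5) |
| >0.5 Giga/L | −0.072 (GM 0.4, s 0.7, r 0.8) | −0.279 (GM 0.3, s 0.9, r 0.5) |

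In relative terms these span +11% to +63% and −8% to −28%. Two gamma models, run as a shape check, gave the same signs (+0.058 and +0.076; −0.079 and −0.118).

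**Visibility.** For GM 0.4, s 0.8, r 0.7 and all 354 children pooled, a simulation gave +0.080 (SE 0.016) and −0.125 (SE 0.054), about 5 and 2.3 standard errors. Single treatment categories would have larger standard errors.

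**Re-anchoring to Week 0**, with grouping still by parent baseline. If the correlation with parent baseline is the same at Week 0 and later, the artifact is zero. If it decays, part remains:

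| Correlation with parent baseline: Week 0, later | Change from parent baseline (low / high) | Change from Week 0 (low / high) |
|---|---|---|
| 0.65, 0.55 (GM 0.4, s 0.7) | +0.100 / −0.166 | +0.023 / −0.038 |
| 0.80, 0.60 (GM 0.4, s 0.8) | +0.108 / −0.168 | +0.055 / −0.087 |

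The first case removes about three-quarters of the artifact (0.023/0.100 remains), the second about half (0.055/0.108 remains).

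**The case against.** The strongest reply is that the artifact is real but its reach is small, and much of that stands.

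- **Shape after Week 0.** Each child's parent baseline is a fixed number. For the same children, change at a visit minus change at Week 0 is simply the change from Week 0. With stable correlation the artifact is one step before or at Week 0 and flat afterwards. A reader might infer that the figure hides a rise occurring during LTS14424. The documents do not support that if the Week 0 point is drawn. The general laboratory rules in SAP 2.4.5 and 2.4.5.3 call for that point, although 2.4.6.2 does not repeat it for this figure.
- **Calibration.** Week 0 precedes any dupilumab for Placebo-Dupilumab children, so their Week 0 change shows regression to the mean plus natural change. The SAP does not tell the reader to use it this way.
- **Other displays.** A reader might infer that this figure is the only planned view of eosinophils by starting level. It is not. The peak-count table covers the same subgroups with absolute values, so the change-score artifact does not apply to it directly. SAP 2.4.5.3 also plans PCSA incidence by status at parent baseline and at Week 0, and profile listings.
- **Net curve.** It is tempting to say that the low curve will rise and the high curve fall. Only the contribution of regression to the mean has a known sign; the plotted curves also carry drug and time effects.
- **Raw means.** Plotting subgroup counts instead of changes looks like a cure but is not. For the same children it is the same curve moved vertically.

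These points limit the consequence. They do not remove the step from the subgroup curves.

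**Conclusion.** The point holds as a limitation of one untested descriptive figure. Grouping on and subtracting the same parent-baseline count adds an upward shift to the ≤0.5 Giga/L curve and a downward shift to the >0.5 curve, mainly as a step between parent baseline and the first LTS14424 value. The direction needs only exchangeable counts and imperfect repeatability. The size rests wholly on the assumed log-normal model: about +0.03 to +0.16 and −0.07 to −0.28 Giga/L. The primary TEAE endpoint is not touched.

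The Japan figure has the same construction. With 13 participants enrolled (Japan SAP 1.1), its two subgroups support little reading in any case.

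**What to change.** In main SAP 2.4.6.2:

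1. Keep the parent-baseline grouping at 0.5 Giga/L.
2. In each subgroup and treatment category, add a panel of mean change from the LTS14424 Week 0 pre-dose count, which the SAP already derives. Note that this removes the artifact fully only if correlation with parent baseline is stable over time.
3. Retain the change-from-parent-baseline curve, show its Week 0 point explicitly, and footnote regression to the mean. It is still needed because Dupilumab-Dupilumab children have already been treated in the parent study by Week 0, so change from Week 0 shows only further change.
4. State that the subgroup curves are to be read against the Placebo-Dupilumab Week 0 change.

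In Japan SAP 3.6.1.3, group by the Visit 0 count and take change from the Visit 1 count. Protocol 17.7.2.9.1.2 and 17.7.2.9.1.3 collect hematology at both visits. Add a note on the small number of participants.

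The cost is SAP wording, one extra panel in the main figure and a reprogrammed Japan figure, with no new data. The downside is a second reference point for the reader to keep apart from the overall change-from-parent-baseline figure.
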